6.2.2 Follow-up for toxicities

Patients whose treatment is interrupted or permanently discontinued due to an adverse event or clinically significant laboratory value, must be followed up at least once a week (or more frequently if required by institutional practices, or if clinically indicated) for 4 weeks, and subsequently at 4-week intervals, until resolution or stabilization of the event, whichever comes first. Clinical experts or specialists, such as ophthalmologist, endocrinologist, dermatologist, should be consulted as deemed necessary. Further guidelines and recommendations for the management of specific study drug induced toxicities (hyperphosphatemia, diarrhea) are provided in **Table 6**. All patients must be followed up for adverse events and serious adverse events for 30 days following the last doses of Infigratinib.

6.2.3 Anticipated risks and safety concerns for the study drug

Eligibility criteria as well as specific dose modification and stopping rules are included in this protocol. Guidelines for prophylactic or supportive treatment for expected toxicities, including management of study-drug induced adverse events, i.e. hyperphosphatemia, renal toxicities are provided in **Table 6**. Refer to preclinical toxicity and or clinical data found in the Infigratinib Investigator Brochure.

6.3 Concomitant medications

The patient must notify the investigational site about any new medications he/she takes after the start of the study drug. All medications (other than study drug) and significant non-drug therapies (including physical therapy, herbal/natural medications and blood transfusions) administered during the study must be listed on the Concomitant Medications eCRF page. A concomitant medication is considered prohibited if it appears on any of the prohibited medication lists for any clinical pharmacology property of the drug (e.g. CYP, BCRP).

6.3.1 Permitted concomitant therapy

Any palliative and supportive care for disease related symptoms, including any medication for a concurrent medical condition are permitted, except as specifically prohibited below.

Hematopoietic growth factors

Hematopoietic growth factors (e.g. erythropoietin, G-colony stimulating factor (CSF) and GM-CSF) are not to be administered prophylactically or to be used to meet eligibility criteria. However, these drugs may be administered as per the label of these agents or as dictated by local practice or guidelines established by the American Society of Clinical Oncology (ASCO).

Hormone replacement therapies

Hormone replacement therapies such as thyroid and growth hormones are allowed, as well as estrogen replacement hormone treatment.

Phosphate-lowering therapy

Phosphate-lowering treatment, including low phosphate diet and phosphate binding therapy, such as sevelamer hydrochloride, should be implemented prophylactically at study drug initiation and modified as clinically indicated throughout Infigratinib administration. Recommendations for treatment are provided in **Table 6**, but should be modified as per country or institutional practice.

6.3.2 Permitted concomitant therapy requiring caution and/or action

Details for specific medications which require action and/or caution while on study are provided in Appendix 1. The rationale for these medications is provided below.

Drugs that alter the pH of the GI tract

Infigratinib is characterized by pH-dependent solubility, and therefore, medicinal products that alter the pH of the upper gastro-intestinal tract may alter the solubility of Infigratinib, and limit bioavailability.

Substrates and inhibitors

CYP substrates and inhibitors

Infigratinib was shown to inhibit the CYP3A4 in in-vitro assays, thus, suggesting an increased risk of drug interactions with concomitant medications that are metabolized by CYP3A4.

Infigratinib is a substrate of CYP3A4. Therefore moderate inhibitors and inducers should be used with caution if no other alternative is available.

Transporter substrates

In vitro data show that Infigratinib is an inhibitor of BCRP (Breast Cancer Resistance Protein). Medications which are BCRP substrates must be monitored for potential toxicity and may require dose titration or reduction of the medication.

Anti-emetics

Anti-emetics are allowed for the treatment of nausea or vomiting. It is recommended to avoid using drugs that are known to cause QT prolongation. Note that some anti-emetics have a known risk for Torsade de Pointes, and therefore need to be used with caution. See Appendix 1 for list of drugs that need to be used with caution. Aprepitant is both a sensitive substrate and a moderate CYP3A4 inhibitor and should be used with caution if an alternative is not available.

Medications with a possible or conditional risk of QT/QTc interval prolongation or torsade de pointes

Preliminary data have shown that Infigratinib has no effect on cardiac conduction or ECG intervals (see current version of the Infigratinib Investigator Brochure). However, medications that have the potential to prolong the QT/QTc interval or induce Torsade de Pointes (possible and conditional risk of TdP/QT prolongation) are allowed with caution. Investigators at their discretion may co-administer such medications, but patients should be carefully monitored. See Appendix 1 for list of drugs that need to be used with caution. Please note that the list might not be comprehensive.

6.3.3 Prohibited concomitant therapy

Details for specific medications prohibited while on study are provided in Appendix 2. The rationale for the restricted medications is provided below.

Other investigational and antineoplastic therapies

Other investigational therapies must not be used while the patient is on the study. Anticancer therapy (chemotherapy, biologic or radiation therapy (that includes > 30% of the bone marrow reserve, and surgery) other than the study treatment must not be given to patients while the patient is on the study medication. If such agents are required for a patient then the patient must be discontinued from the study

CYP inhibitors

Strong inhibitors of CYP3A4 such as the ones listed in Appendix 2 are prohibited because Infigratinib is a likely substrate of this isoenzyme.

CYP inducers

Strong inducers of CYP3A4 are prohibited because their usage may decrease the exposure of Infigratinib. Therefore, agents such as those listed in Appendix 2 are prohibited. Please note that the list may not be exhaustive.

Phosphorus and calcium

Medications that increase the serum levels of phosphorus and/or calcium are prohibited.

Medications with a known Risk of QT/QTc interval prolongation or torsade de pointes

Preliminary data have shown that Infigratinib has no effect on cardiac conduction or ECG intervals (See current version of the Infigratinib Investigator Brochure). However, medications that are known to prolong the QT/QTc interval or induce Torsade de Pointes (Risk of TdP/QT prolongation) are prohibited. List of these medications is given in Appendix 2. Please note that the list might not be comprehensive.

6.4 Patient numbering, treatment assignment or randomization

6.4.1 Patient numbering

Each patient is identified in the study by a Subject Number (Subject No.), that is assigned when the patient is first enrolled for screening and is retained as the primary identifier for the patient throughout his/her entire participation in the trial. The Subject No. consists of the Center Number (Center No.) (as assigned by The Ohio State University to the investigative site) with a sequential patient number suffixed to it, so that each subject is numbered uniquely across the entire database. Upon signing the informed consent form, the patient is assigned to the next sequential Subject No. available to the investigator through The Ohio State University Multi-Site Clinical Trial Team.

6.4.2 Treatment assignment or randomization

This is an open-label, single arm study. There will be no randomization required for this study.

6.4.3 Treatment blinding

Treatment is not blinded in this study.

6.5 Study drug preparation and dispensation

The investigator or responsible site personnel must instruct the patient or caregiver to take the study drugs as per protocol. Study drug(s) will be dispensed to the patient by authorized site personnel only. All dosages prescribed to the patient and all dose changes during the study must be recorded on the Dosage Administration Record CRF.

Infiratinib will be supplied as hard gelatin capsules for oral use of dosage strengths 25 mg, and 100 mg.

6.5.1 Study drug packaging and labeling

Infiratinib capsules are packaged in HDPE bottles with child resistant closures.

Medication labels will be in the local language and comply with the legal requirements of each country. They will include storage conditions for the drug but no information about the patient.

6.5.2 Drug supply and storage

Study treatments must be received by designated personnel at the study site, handled and stored safely and properly, and kept in a secured location to which only the investigator and designated site personnel have access. Upon receipt, the study treatment should be stored according to the instructions specified on the drug labels and in the Investigator's Brochure.

6.5.3 Study drug compliance and accountability

6.5.3.1 Study drug compliance

Compliance will be assessed by the investigator and/or study personnel at each patient visit and information provided by the patient and/or caregiver will be captured in the Drug Accountability Form. This information must be captured in the source document at each patient visit.

6.5.3.2 Study drug accountability

The investigator or designee will maintain an accurate record of the shipment and dispensing of study treatment in a drug accountability log. Patients will be asked to return all unused study treatment and packaging on a regular basis, at the end of the study or at the time of study treatment discontinuation. During the course of the study, the investigator will maintain accurate records of used and unused study treatment, packaging, drug labels, and drug accountability log.

6.5.3.3 Handling of other study treatment

Not applicable.

6.5.4 Disposal and destruction

The study drug can be destroyed at the site if permitted by local regulations. Alternatively, the study drug can be destroyed at a third-party depot.

7. Visit schedule and assessments

7.1 Study flow and visit schedule

Table 7 lists all of the assessments and indicates with an “X” the visits when they are performed. All data obtained from these assessments must be supported in the patient’s source documentation. The table indicates which assessments produce data to be entered into the database (D) or remain in source documents only (S) (“Category” column).

- Baseline imaging assessments can be conducted within 28 days prior to 1st day of study treatment.
- All other baseline/screening assessments must be performed within 21 days prior to 1st treatment.
- Baseline/screening assessments that are conducted within 3 days prior to 1st treatment can be used to satisfy the day 1 requirement. Every effort must be made to follow the schedule outlined in **Table 7**.

For all visits, there is a \pm 3-day window on assessments to take into account scheduling over weekends and holidays, if not explicitly specified otherwise. For post baseline imaging assessments, a \pm 7 day window is allowed, except for the first post baseline assessment (+7 day window permitted).

All assessments should be performed as outlined in **Table 7** and as clinically indicated.

Table 7: Visit evaluation schedule

	Category	Screening	Cycle 1				Cycle 2		Cycle 3		Subsequent cycles	End of study treatment	30-day follow-up (end of study)	Disease Progression follow-up every 8 weeks	Survival follow-up (every 4 months after EOT for 1 year)
Study Period			Treatment									EOT	Follow-up		
Day of Cycle		-28 to -1	1	8	15	21	1	15	1	15	1	≤14 days of decision to discontinue treatment			
Study Informed Consent (ICF)	D	X													
Demography	D	X													
Inclusion/exclusion criteria	D	X													
Relevant medical history/current medical conditions	D	X													
Diagnosis and extent of cancer	D	X													
Prior antineoplastic therapy	D	X													
Prior/concomitant medications	D	X	Continuous									X	X		
Physical examination	S	X	X	X	X	X	X	X	X	X	X	X			
Height	D	X													
Weight	D	X	X				X		X		X	X			
Vital signs	D	X	X	X	X	X	X	X	X	X	X	X			
Performance status	D	X	X				X		X		X	X			
Ophthalmic assessment	D	X			X		X		X		X	X			
Hematology	D	X	X	X	X	X	X	X	X		X	X			
Chemistry	D	X	X	X	X	X	X	X	X		X	X			
Coagulation	D	X	If clinically indicated												
Urinalysis (microscopic or macroscopic)	D	X	If clinically indicated												
Pregnancy test	D	X	X				X		X		X	X			
Tumor response per RECIST 1.1	D	X							X		Day 1 of every odd cycle	X (if not done within 28 days prior)		X (only for pts. who discontinue)	

	Category	Screening	Cycle 1			Cycle 2		Cycle 3		Subsequent cycles	End of study treatment	30-day follow-up (end of study)	Disease Progression follow-up every 8 weeks	Survival follow-up (every 4 months after EOT for 1 year)
Study Period			Treatment									EOT	Follow-up	
Day of Cycle		-28 to -1	1	8	15	21	1	15	1	15	1	≤14 days of decision to discontinue treatment		
													for any reason other than progression of disease	
Study drug administration			Continuous on a 3 weeks on 1 week off schedule											
12-lead ECG	D	X	X		X		X		X		X	X		
Cardiac imaging (ECHO or MUGA)	D	X				X						X		
Adverse Events	D	Continuously throughout the study												
Collection of archival paraffin blocks/slides or a newly obtained tumor sample AND pathology report	D	X												
Newly obtained tumor sample (if medically feasible)	D	X ^a	X (mandatory on-treatment biopsies occurring at the end of Cycle 2 and upon disease progression)											
Blood sample for assessment of circulating tumor DNA (ctDNA)	D	X	X		X		X	X	X	X	Day 1 of every cycle	X (if not done within 28 days prior)		
Survival follow-up	D													X
Antineoplastic therapies since discontinuation of study treatment	D											X	X	
Disease progression follow-up													X	

^a Sample will not be collected if a fresh tumor sample has already been collected at baseline for the purpose of DNA sequencing.

7.1.1 Molecular Eligibility

Evidence of *FGFR* genetic alterations can be obtained from any CLIA-certified assay including but not limited to local testing of samples at an institution-designated or preferred laboratory or an institution-designated sequencing facility.

A copy of the corresponding pathology report for each patient will be sent to the Lead Site (The Ohio State University Multi-Site Clinical Trial Team).

FGFR genetic alterations must be captured on the appropriate eCRF upon enrollment onto the study after the patient has signed the study's main Informed Consent.

In addition, all patients will provide a pre-treatment tumor specimen, preferably a tumor biopsy, so that subsequent central testing and analysis can be completed.

7.1.2 Screening

The IRB study approved informed consent form (ICF) must be signed and dated before any study-specific screening procedure is performed. Procedures which are part of the clinical routine during the initial diagnostic work-up of the patient may be obtained before obtaining the ICF. A copy of the ICF must be given to the patient or to the person signing the form. The investigator or designee must record the date when the study informed consent was signed in the medical records of the patient.

Patients will be evaluated against study inclusion and exclusion criteria and safety assessments. Screening assessments must be completed within 21 days prior to the first dose of treatment except for the radiological tumor assessment which should be performed within 28 days prior to the first dose. Screening assessments must be repeated if outside of screening windows.

7.1.2.1 Eligibility screening

After a patient signs the study Informed Consent Form, the investigator or clinical site should determine patient eligibility.

7.1.2.2 Information to be collected for screen failures

The reason for not being started on study treatment will be entered on the screening phase disposition page. For all screening failure patients, demography, inclusion/exclusion and informed consent information along with the reason for screen failure will be collected. No other data will be entered in the database for patients who are screen failures, unless the patient experienced a Serious Adverse Event during the screening phase (see Section 8 for SAE reporting details).

7.1.2.3 Patient demographics and other baseline characteristics

Data to be collected will include general patient demographics, relevant medical history and current medical conditions, prior concomitant medications, diagnosis and extent of tumor, baseline tumor

mutation status (FGFR gene fusions/translocation or other FGFR genetic alterations) and details on prior antineoplastic treatments.

7.1.3 Treatment period

The treatment period commences on the first day of the first cycle of Infigratinib and ends after the last dose of Infigratinib.

During the study treatment period, patients will be regularly monitored to assess the safety and early anti-tumor activity of treatment. For purpose of scheduling and evaluations, a treatment cycle will consist of 28 days.

During the treatment period, the patient is obliged to follow the investigators instructions with regards to contraception, concomitant medications and dosing regimen. There is no fixed duration; patients may continue treatment with the study drug until the development of an unacceptable toxicity that precludes any further treatment, disease progression, and/or treatment is discontinued at the discretion of the Investigator or by patient refusal.

7.1.4 Discontinuation of study treatment

Patients may voluntarily discontinue from the study treatment for any reason at any time. If a patient decides to discontinue from the study treatment, the investigator should make a reasonable effort (e.g. telephone, e-mail, letter) to understand the primary reason for this decision and record this information in the patient's chart and on the appropriate CRF pages. They may be considered withdrawn if they state an intention to withdraw, fail to return for visits, or become lost to follow-up for any other reason.

Study treatment must be discontinued under the following circumstances:

- Adverse events, that results in a significant risk to the patient's safety.
- The following deviation from the prescribed dose regimen for study treatment: dose interruption of > 14 days from the intended day of the next scheduled dose, unless otherwise specified in Section 6.1.3
- Pregnancy
- Any other protocol deviation that results in a significant risk to the patient's safety
- Patients who discontinue study treatment should NOT be considered withdrawn from the study. They should return for the assessments indicated in **Table 7** (end of study treatment visit) and then enter the follow-up epoch. If they fail to return for these assessments for unknown reasons, every effort (e.g. telephone, email, letter) should be made to contact them (Lost to follow-up).

For patients who discontinue treatment for reasons other than documented disease progression, death, lost to follow-up, or withdrawal of consent, tumor assessments must continue to be performed every 8 weeks until documented disease progression, death, lost to follow-up, or withdrawal of consent.

7.1.4.1 Replacement policy

No replacements will be needed.

7.1.5 Withdrawal of consent

Patients may voluntarily withdraw consent to participate in the study for any reason at any time. Withdrawal of consent occurs only when a patient does not want to participate in the study any longer, and does not want any further visits or assessments, and does not want any further study related contact.

The Lead Investigative Site (The Ohio State University) will continue to retain and use all research results that have already been collected for the study evaluation. All biological samples that have already been collected may be retained and analyzed at a later date (or as required by local regulations).

If a patient withdraws consent, the investigator must make every effort (e.g. dates of telephone calls, e-mail, letter) to determine the primary reason for this decision and record this information.

Study treatment must be discontinued, and no further assessments conducted.

Further attempts to contact the patient are not allowed unless safety findings require communication or follow-up.

7.1.6 Follow-up period

Patients lost to follow-up should be recorded as such on the eCRF. For patients who are lost to follow-up, the Investigator should show "due diligence" by documenting in the source documents steps taken to contact the patient, e.g. dates of telephone calls, registered letters, etc.

30-day safety follow-up period

All patients must complete the safety follow-up assessments 30 days after the last dose of the study treatment. Information relating to antineoplastic therapies taken since discontinuation of study treatment and AEs (including concomitant medication taken for ongoing AEs) will be collected for 30 days after the last dose of the study treatment.

All AEs suspected to be related to study drug should be followed up weekly, or as clinically indicated, until resolution or stability.

Disease progression follow-up period

All patients enrolled in the study who discontinue study treatment for any reason other than disease progression will have a tumor assessment every 8 weeks (\pm 7 days), until disease progression or the initiation of subsequent anticancer therapies, or death, whichever occurs first. Any newly started antineoplastic therapies during the follow-up period must be recorded on the Antineoplastic therapy since discontinuation eCRF.

Survival follow-up period

All patients enrolled in the study will be followed for survival every 4 months for one year after discontinuation of treatment. Survival follow-up will continue until all patients have discontinued study and at least 80% of the patients have died, withdrawn consent, or been lost to follow-up.

7.1.7 Lost to follow-up

For patients whose status is unclear because they fail to appear for study visits without stating an intention to withdraw consent, the investigator should show "due diligence" by contacting the patient, family or family physician as agreed in the informed consent and by documenting in the source documents steps taken to contact the patient (e.g. dates of telephone calls, emails, letters, etc.). A patient should not be considered lost to follow-up until due diligence has been completed.

7.2 Assessment types

7.2.1 Efficacy assessment

Tumor response will be evaluated locally by the investigator according to the guideline (see Appendix 3) based on the Response Evaluation Criteria in Solid Tumors (RECIST) Version 1.1 (Eisenhauer et al 2009). Each patient will be evaluated for all potential sites of tumor lesions at screening/baseline and every 8 weeks after starting study treatment until disease progression.

CT (Computed Tomography) /MRI (Magnetic Resonance Imaging) scans will be performed at baseline within 28 days before start of treatment and subsequently every 8 weeks from treatment start until progression of disease.

After baseline, the first assessment should be performed at Cycle 3 Day 1 (+7 day window) and all subsequent assessments should be performed within ± 7 days of the scheduled day of assessment. The same method of assessment and the same technique should be used to characterize each individual and reported lesion at baseline and during follow-up. If a patient discontinues treatment for reasons other than radiological documentation of progression of disease, an efficacy assessment should be performed at the time of End of Treatment unless a CT/MRI for tumor measurement was performed ≤ 4 weeks earlier.

Chest, abdomen, and pelvis CT scans are required for all patients at baseline. If at baseline, a patient is known to have a contraindication to CT i.v. contrast media or develops a contraindication during the trial, a contrast-enhanced MRI (if possible) of chest, abdomen, and pelvis should be performed.

For the patients with skeletal lesions suspected at baseline, a whole-body bone scan (e.g. TC 99, NaF PET, etc.) should be performed. Skeletal lesions which are identified on a whole body bone scan at baseline, which are not visible on the chest, abdomen or pelvis CT/MRI scan, should be re-imaged at baseline with localized CT, MRI or x-ray, and followed at scheduled visits (every 8 weeks).

Partial Response (PR) and Complete Response (CR) should be confirmed by repeat assessments performed at least 4 weeks and no later than 6 weeks after the criteria for response are first met.

PET/CT may be used only if it is of similar diagnostic quality as a CT performed without PET, including the utilization of oral and intravenous contrast media. While FDG-PET may complement CT scans in assessing progression per RECIST 1.1 (Appendix 3) FDG-PET assessments should be disregarded for this protocol.

If possible, a single radiologist should perform all tumor response evaluations for an individual patient.

Any lesion that has been previously treated with radiotherapy should be considered as a nontarget lesion. However, if a lesion previously treated with radiotherapy has clearly progressed since the radiotherapy, it can be considered as a target lesion.

All radiological assessments obtained for patients enrolled during the study will be sent to The Ohio State University Multi-Site Clinical Trial Team.

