4.4 Definition of end of the study

End of study is defined as the time when the last patient completes the survival follow-up as described in Section 7.1.6 or when the last patient on study has expired, been lost to follow-up, or withdraws consent, whichever occurs first or when the study is terminated early.

The analysis of study data will be based on all patients' data up to the time when all patients have completed at least 6 cycles of treatment or discontinued the study. This will be the cutoff point for the primary clinical study report (CSR). The additional data for any patients continuing to receive Infigratinib, or remain in safety or survival follow-up beyond the cut-off point will be summarized in a final CSR that will be prepared once all patients have either discontinued or completed the study i.e. end of survival follow-up period which is defined as the time when all patients have discontinued study and at least 80% of the patients have died, withdrawn consent, or been lost to follow-up.

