13.3.17 Best overall response

The best overall response is the best response recorded from the start of the treatment until disease progression/recurrence (taking as reference for PD the smallest measurements recorded since the

treatment started). In general, the patient's best response assignment will depend on the achievement of both measurement and confirmation criteria.

The best overall response will usually be determined from response assessments undertaken while on treatment. However, if any assessments occur after treatment withdrawal the protocol should specifically describe if these will be included in the determination of best overall response and/or whether these additional assessments will be required for sensitivity or supportive analyses. As a default, any assessments taken more than 30 days after the last dose of study treatment will not be included in the best overall response derivation. If any alternative cancer therapy is taken while on study any subsequent assessments would ordinarily be excluded from the best overall response determination. If response assessments taken after withdrawal from study treatment and/or alternative therapy are to be included in the main endpoint determination, then this should be described and justified in the protocol.

Where a study requires confirmation of response (PR or CR), changes in tumor measurements must be confirmed by repeat assessments that should be performed not less than 4 weeks after the criteria for response are first met.

Longer intervals may also be appropriate. However, this must be clearly stated in the protocol. The main goal of confirmation of objective response is to avoid overestimating the response rate observed. In cases where confirmation of response is not feasible, it should be made clear when reporting the outcome of such studies that the responses are not confirmed.

- For non-randomized trials where response is the primary endpoint, confirmation is needed.
- For trials intended to support accelerated approval, confirmation is needed
- For all other trials, confirmation of response may be considered optional.

The best overall response for each patient is determined from the sequence of overall (lesion) responses according to the following rules:

- CR = at least two determinations of CR at least 4 weeks apart before progression where confirmation required or one determination of CR prior to progression where confirmation not required

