- PR = at least two determinations of PR or better at least 4 weeks apart before progression (and not qualifying for a CR) where confirmation required or one determination of PR prior to progression where confirmation not required
- SD = at least one SD assessment (or better) > 6 weeks after randomization/start of treatment (and not qualifying for CR or PR).
- PD = progression \leq 12 weeks after randomization/ start of treatment (and not qualifying for CR, PR or SD).
- UNK = all other cases (i.e. not qualifying for confirmed CR or PR and without SD after more than 6 weeks or early progression within the first 12 weeks)

Overall lesion responses of CR must stay the same until progression sets in, with the exception of a UNK status. A patient who had a CR cannot subsequently have a lower status other than a PD, e.g. PR or SD, as this would imply a progression based on one or more lesions reappearing, in which case the status would become a PD.

Once an overall lesion response of PR is observed (which may have to be a confirmed PR depending on the study) this assignment must stay the same or improve over time until progression sets in, with the exception of an UNK status. However, in studies where confirmation of response is required, if a patient has a single PR ($\geq 30\%$ reduction of tumor burden compared to baseline) at one assessment, followed by a $<30\%$ reduction from baseline at the next assessment (but not $\geq 20\%$ increase from previous smallest sum), the objective status at that assessment should be SD. Once a confirmed PR was seen, the overall lesion response should be considered PR (or UNK) until progression is documented or the lesions totally disappear in which case a CR assignment is applicable. In studies where confirmation of response is not required after a single PR the overall lesion response should still be considered PR (or UNK) until progression is documented or the lesion totally disappears in which case a CR assignment is applicable.

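### The 4-to-6-week confirmation window in 7.2.1 does not match the 8-weekly scans or the confirmation rule in Appendix 3, and no text says which rule governs the primary ORR

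*Combined protocol and SAP*

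**What the plan says.** - **Confirmation, protocol body (7.2.1).** Both CR and PR "should be confirmed by repeat assessments performed at least 4 weeks and no later than 6 weeks after the criteria for response are first met".
- **Scan calendar (7.2.1).** After baseline, CT/MRI is done "subsequently every 8 weeks from treatment start until progression of disease". The first post-baseline scan is at Cycle 3 Day 1. The windows are ± 7 days "except for the first post baseline assessment (+7 day window permitted"), and 7.2.1 repeats that "all subsequent assessments should be performed within ± 7 days of the scheduled day of assessment".
- **Table 7 (7.1).** The tumor-response row shows screening, C3D1, "Day 1 of every odd cycle", end of treatment, and 8-weekly follow-up for patients who stop for reasons other than progression. It has no confirmation scan and no footnote for one.
- **Confirmation, Appendix 3 (13.3.17).** Confirmation is needed in a non-randomized trial with response as primary endpoint. The rule is "PR = at least two determinations of PR or better at least 4 weeks apart before progression", with no maximum. On timing it adds: "Longer intervals may also be appropriate. However, this must be clearly stated in the protocol". Its worked example (PR, then SD, then PR) counts as confirmed.
- **Primary analysis (10.4.1).** Every PR or CR up to the data cut-off makes the patient a responder. Confirmation is not mentioned.
- **Cut-off (4.4; same condition in 10.4.1).** Data are analyzed "up to the time when all patients have completed at least 6 cycles of treatment or discontinued the study". Later data go into a final report.
- **Decision rules for Cohort 1 (10.1).** Stop after 9 patients if none responds; otherwise enroll 30 and call the drug promising with 4 or more responders. Stated power is 90% and type I error 5%.

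**The concern.** Take a patient with PR at C3D1 and again at C5D1, both on the nominal day. Under 13.3.17 this is a confirmed PR. Under 7.2.1 the second scan is two weeks late. Under 10.4.1 the patient is a responder either way, because confirmation is not mentioned. Section 7.2.1 itself refers assessors to Appendix 3, so both timing rules are in force at once and neither is ranked above the other.

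This patient represents what a site will usually produce if it follows Table 7. In Cohort 1 one responder is enough to pass stage 1 and four are enough at the end, so reclassifying one or two patients can change the conclusion. The trial is open-label with investigator-assessed response. If the rule is left open, someone will have to choose it after the responses are known.

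**Working it through.** **1. The plan's own design figures.** Inputs from 10.1: null ORR p = 0.05, alternative p = 0.25, n1 = 9, stop at 0/9, N = 30, success at 4 or more.

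P(success) = sum over x = 1 to 9 of P[Bin(9, p) = x] × P[Bin(21, p) ≥ 4 − x].

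- p = 0.05: 0.0489, within the stated 5%.
- p = 0.25: 0.902, as stated (90%).

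The design itself is not in dispute.

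**2. When scheduled scans fall.** Cycles are 28 days; treatment starts on day 1.

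| Scan | Nominal day | With window |
|---|---|---|
| C3D1 | 57 | 57–64 |
| C5D1 | 113 | 106–120 |
| C7D1 | 169 | 162–176 |

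**3. Gap between consecutive scheduled scans.**

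- Nominal: 113 − 57 = 56 days, which is 14 days beyond the 42-day maximum.
- First pair: shortest 106 − 64 = 42, longest 120 − 57 = 63.
- Later pairs: shortest 56 − 14 = 42, longest 56 + 14 = 70.

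Counting whole-day combinations, the first pair has 8 × 15 = 120 and a later pair 15 × 15 = 225. In each, exactly one combination (first scan at +7, next at −7) gives a gap of 42 days or less. These are counts of possibilities, not probabilities. Every scheduled gap exceeds the 28-day minimum of 13.3.17.

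**4. The cut-off.** Six cycles end on day 6 × 28 = 168. With confirmation timed as in 7.2.1, a PR first seen at C5D1 (day 106–120) is confirmed between day 106 + 28 = 134 and day 120 + 42 = 162, before the cut-off condition can be met. If confirmation may instead wait for C7D1, the nominal day is 169, one day after it.

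**5. Illustration of enforcing the limit.** Suppose a response confirmed after 42 days were not counted, and a share f of true responders had no scan in weeks 4 to 6. The documents give no value for f; it is assumed. The countable ORR is 0.25 × (1 − f), entered in the formula of step 1. The chance of a stage 1 stop is (1 − countable ORR)^9.

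| f (assumed) | Countable ORR | Power | Chance of 0/9 |
|---|---|---|---|
| 0% | 25% | 0.902 | 0.075 |
| 20% | 20% | 0.793 | 0.134 |
| 30% | 17.5% | 0.704 | 0.177 |
| 40% | 15% | 0.588 | 0.232 |

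**The case against.** The strongest reply is that 7.2.1 can be read as ordering a response-triggered scan on top of the 8-week calendar. Section 7.1 also allows assessments as clinically indicated, and an end-of-treatment scan might fall in the window by chance. This stands in part. A reader might infer that the window cannot be met at all, and the documents do not support that. What remains is that the schedule sites are told to follow does not include the scan.

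A second reply is that no passage excludes a response confirmed after week 6. The wording in 7.2.1 is advisory, no consequence is attached, and neither 13.3.17 nor 10.4.1 applies a maximum. This also stands. A reader might infer that such responses will be dropped from the 4/30 count; that is a possible application of 7.2.1, not a stated rule. It follows that the power figures are not expected losses. They need an exclusion rule that is not written and fractions that are not given.

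A third reply concerns the cut-off. A reader might infer that the plan as written already loses late responses there. Step 4 shows otherwise for a PR first seen at C5D1 and confirmed on the 7.2.1 timing. Six cycles is also a minimum, C7D1 may be done from day 162, and later data go to the final report. The cut-off matters mainly once confirmation is allowed at the next scheduled scan.

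Lastly, the 13.3.17 remark on longer intervals follows a minimum, so it may mean a longer minimum. The worked example has no dates and says nothing about a maximum. The point does not depend on either.

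**Conclusion.** The inconsistency is real and bears on the primary endpoint. Section 7.2.1 sets a maximum that the next scheduled scan meets only in one edge case, Appendix 3 sets none, 10.4.1 does not mention confirmation, and nothing ranks the three. This rests on the text and on calendar arithmetic alone.

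Its numerical effect cannot be derived from the documents. If the rules are aligned so that the next 8-weekly scan can confirm, the design keeps power 0.902 and type I error 0.0489. If the maximum were enforced without a scheduled scan, the loss would depend on the unknown share of responders with no scan in weeks 4 to 6; the 79%, 70% and 59% figures show sensitivity only. The plan should be corrected before responses are adjudicated.

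**What to change.** 1. **7.2.1:** delete the 6-week maximum. State that a PR or CR is confirmed by any later assessment that again meets the criteria, at least 4 weeks after they were first met and before progression, as in 13.3.17. Do not tie confirmation to the next scheduled scan, because that would reject the PR-SD-PR sequence that Appendix 3 accepts.
2. **10.4.1:** state that ORR counts responses confirmed by this rule.
3. **4.4 and 10.4.1, as a consequence of item 1:** let the data cut-off include the next scheduled scan (C7D1 or later) for any response still awaiting confirmation.

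**Cost.** These are wording changes and add no scans. Confirmation may come about 2 to 4 weeks later (week 8 instead of week 6 or 4). The cut-off may move by about 1 week (C7D1 by day 176, against day 168) to about 9 weeks (a response first seen at C7D1 and confirmed at C9D1, nominal day 169 + 56 = 225, latest day 232; 232 − 168 = 64 days).

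Adding a response-triggered scan at 4 to 6 weeks to Table 7 would also close the schedule gap without moving the cut-off. It costs extra imaging, and 10.4.1 would still need to name the governing rule.
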